Even though there is a lack of pharmacologically-relevant animal models for the evaluation of Betolutin mechanism of action or safety studies there is a considerable clinical experience with CD37 targeted antibodies, ¹⁷⁷Lu radiolabelled agents and the DOTA chelator. Human experience is considered more relevant to the development of Betolutin and can provide significant insight into the anticipated clinical response. ¹⁷⁷Lu-labelled rituximab, prepared using the same DOTA procedure as for Betolutin, has recently been administered clinically (30, 31). The maximum tolerated dose was 50 mCi/m² (approximately 48 MBq/kg body weight) and efficacy results in NHL patients were promising. This report confirms that the radiolabelling procedure for Betolutin is compatible with human administration and provides supportive evidence of the safety of both satetraxetan and ¹⁷⁷Lu.

It is anticipated that benefits of administration of the IMP will include a targeted antitumour response, evidenced by improvements in progression-free survival and OS. Furthermore, the targeted binding of lilotomab to CD37 expressed on lymphoma cells is anticipated to increase delivery of ¹⁷⁷Lu to the desired site of action, thus minimising general systemic toxicity typically associated with external radiation therapy.

Risk with rituximab pre-treatment

The most frequently observed adverse drug reactions (ADRs) in patients receiving MabThera® are infusion-related reactions which occur in the majority of patients during the first infusion. The incidence of infusion-related symptoms decreases substantially with subsequent infusions and is less than 1% after 8 doses of MabThera. Infectious events (predominantly bacterial and viral) occurred in approximately 30-55% of patients during clinical studies in patients with NHL. ADRs reported as very common (≥1/10) are infections (bacterial and viral), reduction in haematological parameters, infusion-related reactions such as angioedema, nausea, pruritus, rash, alopecia, fever, chills, asthenia, headache, and decreased immunoglobulin G (IgG) levels. Please refer to the prescribing information for further details.

Risk with lilotomab pre-dosing

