3.3 Derived Data

- *Definition of study day*

Study day is relative to the date of first administration of Betalutin and lilotomab (study Day 1). Therefore, study day for rituximab will be negative.

Note: in the protocol, Betalutin administration day is referred to as Day 0. However, for statistical analysis and to be in line with CDISC requirement, Betalutin administration day will be defined as Day 1, the day before Day 1 is defined as Day -1 and there is no Day 0.

- *Definition of baseline*

Study baseline is defined as the last non-missing value (including scheduled and unscheduled assessments) prior to rituximab dosing. This will usually be the latest value collected at the screening visit.

Betalutin baseline is defined as the last value measured prior to lilotomab and Betalutin dosing. A visit window from day -2 to day 1 (prior to lilotomab and Betalutin dosing) will be used.

- *Incomplete dates*

For calculation purposes, incomplete dates will generally be completed using worst case. For example, the 15th of the month will be used when day is missing and 1st July when day and month are missing.

Further details are given in the relevant sections as required.

- *Non-numeric values*

In the case where a variable is recorded as “>x”, “≥x”, “<x” or “≤x”, then for analysis purposes a value of x will be taken. Where a range of values is quoted the midpoint of the range will be taken.

- *Month windows*

For the laboratory values and change from baseline outputs, to take account of the potential for out of window assessments being conducted due to the COVID-19 pandemic, the following Month labels will be rederived using the table below.

Table 3: LYMRIT-37-01 study, Part B Month Windows

Month	Days relative to the date of Betalutin administration *
Week 8	Days 53 to 61

Week 12	Days 81 to 89
Month 3	Days 78 to 122
Within the first 3 Months	Days 1 to 122
Within the first 6 Months	Days 1 to 213

* (Date of assessment – date of Betalutin administration) +1 if date of assessment is on or after date of Betalutin administration. Otherwise (Date of assessment – date of Betalutin administration).

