3.4 Data Presentation

The TFLs will present the dose regimens (where relevant) as detailed below:

Table 4: LYMRIT-37-01 study, Part B/C Treatment Group Descriptors

Order	Descriptor for Dose Regime (where relevant) to be presented in TFLs	Meaning of Descriptor
1 [1]	40 / 12.5	40 mg lilotomab plus 12.5 MBq/kg Betalutin
2	40 / 15	40 mg lilotomab plus 15 MBq/kg Betalutin
3	100 / 20	100 mg/m ² lilotomab plus 20 MBq/kg Betalutin
4 [1]	Received Rituximab only	Received Rituximab only
5 [1]	Enrolled no treatment	Enrolled but did not receive any trial treatment
6 [1]	Screen failure	Participants in the screened set who failed screening (i.e. are not eligible to join the study per the eligibility eCRF page).

[1] In table summaries, if there is insufficient space to present all treatment groups on a single page, these dose regimens will be presented on the next page.

The data will be summarised in tabular form by Study Part (i.e. B / C) and dose regimen.

Results from scheduled visits will be tabulated. Unscheduled visits will be included in assessments of maximum post-baseline. All assessments will be listed.

Table 5: Populations to be used for output

Type of data	Listings	Summaries
Disposition	Screened set	Screened set
Demographic characteristics and baseline	SAF	SAF, Efficacy Analysis Set
Efficacy	SAF	Efficacy Analysis set

AE's and lab data	SAF	SAF
-------------------	-----	-----

Listings will be sorted by Study Part (i.e. B / C) and dose regimen, patient number and date/time of assessment.

Graphical presentations of the data will also be provided where appropriate.

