3.8.1.1 Treatment-Emergent Adverse Events

The focus of AE summarisation will be on treatment-emergent adverse events (TEAE).

Treatment-emergent adverse events AEs (TEAEs) are defined as those adverse events (AEs) occurring after first administration of rituximab or starting prior to the first administration and worsening during treatment. Adverse events with unknown onset date/time will be considered to be treatment-emergent unless the stop date/time is known to be before first administration of rituximab.

A treatment related TEAE is defined as a TEAE that is possibly or probably or definitively/certainly related to the study treatment (Betalutin, rituximab or lilotomab). If the TEAE has a missing relationship it is assumed to be related to the study treatment for analysis

purposes. This will also be derived separately for Betalutin, rituximab and lilotomab. If the TEAE has a missing relationship it is assumed to be related to all applicable study treatments for analysis purposes.

AEs will be classed as occurring in one of five periods:

- Pre-treatment - any AE that starts after the participant has provided written informed consent and that resolves prior to the first administration of rituximab, or an AE that starts prior to the first administration of rituximab and does not increase in severity after the first administration of rituximab.
- Baseline Period: any AE that starts after the participant has the first administration of rituximab but prior to the first administration of lilotomab or Betalutin (study Day 1).
- Lilotomab/Betalutin Exposure Period: any AE that occurs after the first administration of lilotomab or Betalutin (study Day 1) and upto, and including Day 92, or that is present prior to the first administration of lilotomab or Betalutin and worsens after the first administration of lilotomab or Betalutin.
- Rituximab Exposure Period: relates to the combined Baseline Period and Lilotomab/Betalutin Exposure Period (i.e. all AEs that start after the first administration of rituximab).
- Post Betalutin follow-up period: any AE which starts more than 92 days after the start of Betalutin.

All pre-treatment AEs will be excluded from the tabulations but will be fully listed.

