3.8.1.2 Baseline Period Adverse Events

A table will present the number of events and the number and percentage of participants experiencing TEAEs occurring during the baseline period by SOC and PT.

The table will contain an overall summary and will not be split by actual dose regime. SOC and PT will be presented in descending frequency. If a participant experiences more than one TEAE, the participant will be counted once for each SOC and once for each PT.

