3.8.1.3 Lilotomab/Betalutin Exposure Period Adverse Events

The following tables will present the number of events and the number and percentage of participants experiencing TEAEs by SOC and PT for the following break points with separate summaries being produced for each:

- TEAE onset from Day 1 onwards
- TEAE onset from Day 1 to Day 92 (Month 3)

Each table will contain an overall summary. SOC and PT will be presented in descending frequency of the total number of participants with TEAEs. If a participant experiences more than one TEAE, the participant will be counted once for each SOC and once for each PT.

Table 6: LYMRIT-37-01 study, Part B and C Adverse Event Summary Tables

Summary Table	AE onset from Day 1 onwards	AE onset from Day 1 to Day 92 (Month 3)
TEAEs by SOC and PT	X	X
Serious TEAEs	X	X
Study drug related TEAEs (Betalutin, rituximab or lilotomab)		X
Serious study drug related TEAEs (Betalutin, rituximab or lilotomab)		X
TEAEs by CTCAE grading		X
most frequent TEAEs (reported in at least 5% of participants)		X

Adverse event data will be listed in full and will also include a treatment emergent flag (will distinguish pre-treatment, baseline, post treatment (day 93+), an AESI flag, the time of onset and cessation of event relative to first administration of each of rituximab, Lilotomab and Betalutin and duration of AE. Where CTCAE grade changes over time, the worst/most severe will be reported in summary tables.

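### Serious, related and CTCAE-graded events that start in the rituximab lead-in appear in no summary by those attributes, because every SAP Table 6 summary starts at Day 1 although TEAEs are defined from rituximab

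*SAP*

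**What the plan says.** SAP 3.8.1.1 starts the treatment-emergent clock at rituximab: TEAEs are "defined as those adverse events (AEs) occurring after first administration of rituximab or starting prior to the first administration and worsening during treatment". The same section sets up several reporting periods. One is a Rituximab Exposure Period, which "relates to the combined Baseline Period and Lilotomab/Betalutin Exposure Period (i.e. all AEs that start after the first administration of rituximab"). It also derives relatedness separately for Betalutin, rituximab and lilotomab.

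Day 1 is a different date. SAP 3.3 ties it to lilotomab and Betalutin and adds: "Therefore, study day for rituximab will be negative". SAP 3.6.5.2 places the single rituximab dose on Day -14.

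The planned adverse event tables are:

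- **SAP 3.8.1.2:** one table of events and of "participants experiencing TEAEs occurring during the baseline period by SOC and PT", pooled over regimens.
- **SAP 3.8.1.3, Table 6:** six summaries, each restricted to onset from Day 1. One of them is "Study drug related TEAEs (Betalutin, rituximab or lilotomab").

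The Safety Analysis Set (SAP 3.2.3) takes in anyone given rituximab, lilotomab or Betalutin, and SAP Table 4 has a display group "Received Rituximab only". Adverse event summaries use that set (SAP Table 5), with percentages based on all its members (SAP 3.1). SAP 3.8.1 says that all Part B and Part C patients will be in the adverse event tables.

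Protocol 14.1.10 plans tabulation by CTCAE grade and by relationship, plus separate SAE tables, and sets no Day 1 limit.

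**The concern.** The SAP defines treatment-emergent one way and then tabulates the attributes that matter most for safety over a shorter period. A reader of the abbreviated report who wants to know how many patients had a serious, drug-related or grade 3 or higher event under the whole regimen (rituximab, lilotomab, Betalutin) will look to Table 6. That table cannot answer for the first two weeks.

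The sharpest case is a patient whose serious reaction to rituximab ended further dosing. That patient is in the Safety Analysis Set but would appear in no serious, related or graded summary. The related-event row adds to the problem, because its label suggests that rituximab-related events are covered from the time rituximab is given.

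**Working it through.** No sample size, power or event count is involved, and the plan states no figure to reproduce. The check compares time windows and denominators.

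**1. Windows in Table 6**

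| Summary | Day 1 onwards | Day 1 to 92 | From rituximab |
|---|---|---|---|
| All, by SOC and PT | yes | yes | no |
| Serious | yes | yes | no |
| Study-drug related | no | yes | no |
| Serious and related | no | yes | no |
| By CTCAE grade | no | yes | no |
| Most frequent (5% or more) | no | yes | no |

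Six of six summaries start at Day 1 and none starts at rituximab.

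**2. What covers the lead-in.** Only the SAP 3.8.1.2 table does. It gives the lead-in counterpart of the first row above. It gives nothing for the serious, related, serious related or graded rows.

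**3. Length of the omitted window**

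- Lead-in: Day -14 to Day -1 = 14 days, since SAP 3.3 has no Day 0.
- Exposure window: Day 1 to Day 92 = 92 days.
- Share: 14 / (14 + 92) = 14/106 = 13.2%.
- With the ±2 days that SAP 2.1.1 allows for the dosing visit: 12/104 = 11.5% to 16/108 = 14.8%.

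This share applies only to the Day 1 to 92 columns. It has no meaning for the open-ended column used for all TEAEs and serious TEAEs.

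**4. Rituximab-only patients.** Study day is relative to lilotomab/Betalutin, which these patients never received. They have no Day 1, so no event of theirs can satisfy onset from Day 1. Let the Safety Analysis Set hold N patients, of whom r had rituximab only, and let x patients have a qualifying Table 6 event. The overall column then shows x/N, although only N − r patients could contribute. The dilution factor is (N − r)/N. The documents do not give r. The 40/15 and 100/20 columns are unaffected, because rituximab-only is a separate group.

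**5. Events that cross Day 1.** SAP 3.8.1.1 places an event already present before lilotomab/Betalutin in the exposure period if it worsens afterwards. Table 6 selects on onset. The two rules give different answers for such an event, and the SAP does not say which one governs.

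**6. Disclosure.** SAP 3.10 says in general terms that the analysis is abbreviated. It does not mention this restriction.

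**The case against.** The best defence is that this is an open split by period in a close-out SAP for a terminated study. Table 6 sits under a heading that names the lilotomab/Betalutin exposure period, and each column states its window. Focusing on toxicity after the radioconjugate is legitimate. Pooling the lead-in table over regimens is also reasonable, since nobody has yet received lilotomab or Betalutin at that point. All events are listed with a flag that separates baseline events and with onset relative to rituximab. Deaths are listed, and SAE raw data are supplied. All of this stands, and it rules out any claim that lead-in events are suppressed. It does not supply the missing counts by seriousness, relatedness and grade.

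Three stronger readings are tempting and are not supported:

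- **That every lead-in event and every rituximab-only event goes untabulated.** Lead-in events are in the 3.8.1.2 table. Rituximab-only events plausibly fall there too, although the period definition presumes a later dose. Events that worsen after Day 1 dosing may reach Table 6.
- **That a wave of first-infusion reactions is excluded.** Protocol 4.4 does describe "infusion-related reactions which occur in the majority of patients during the first infusion", but goes on to say that the incidence falls substantially with later infusions. Part B patients must already have had rituximab or another anti-CD20 agent (Protocol 7.1.2, criterion 4).
- **That incidences are understated by 5 to 10 points.** This assumes that 5–10% of patients have a serious or grade 3 or higher lead-in event, a rate the documents do not give, and that none of them has a later event in the same row. Part A had grade 3/4 neutropenia in 56% at 40/15 (Protocol Table 4-5). Suppose a similar share had a graded event after Day 1, independently of the lead-in. The any-grade-3-or-higher figure would then rise by at most 0.44 × 5% = 2.2 to 0.44 × 10% = 4.4 points. That is an illustration and not an estimate.

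**Conclusion.** The gap is real but narrower than a general omission. Under the SAP as written, events with onset between rituximab and Day 1 are counted in no summary by seriousness, relatedness, both together, or CTCAE grade. This is inconsistent with the SAP's own TEAE definition, leaves its Rituximab Exposure Period unused, and departs without explanation from Protocol 14.1.10. In addition, rituximab-only patients enlarge the overall Table 6 denominator and can never enter its numerators.

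The direction is known: serious, related and graded incidences for the full regimen can only be too low. The amount is not known. It depends on how many patients had such a lead-in event without a later one in the same row, and on the number of rituximab-only patients. Neither count is in the documents. The 13.2% is a share of nominal days and should not be read as a share of events. The conclusion assumes that Table 6 is applied by onset as written. It is worth correcting, because the data are collected (Protocol 9.6.2.1 has events after rituximab recorded) and the period is already defined.

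**What to change.** 1. Produce the serious, related, serious related and CTCAE-graded TEAE summaries over the Rituximab Exposure Period as well, in the Safety Analysis Set, with the rituximab-only group shown. Keep the Day 1 tables as they are; they need not become secondary.
2. If that is too much for an abbreviated report, the minimum is to add seriousness, relatedness and grade to the SAP 3.8.1.2 table, and to say that rituximab-only events are included there.
3. State how Table 6 counts a lead-in event that worsens after Day 1.
4. Record the Day 1 restriction in SAP 3.10.

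The cost is SAP wording and a few more runs of table programs already planned, with no new data. The reported incidences may become slightly less favourable.

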13.2 Reporting of Adverse Events

Any AEs that occur after a patient has signed the Informed Consent Form and up to 12 weeks after Day 0, must be reported, whether or not it is considered related to any of the study medications.

After 12 weeks post last administration of study treatment, only new onset AESIs, and study treatment-related AEs and SAEs must be reported when they come to the investigator's attention.

All AEs will be reported in the patient eCRFs. If more than one AE occurs, each event should be recorded separately. AEs and/or laboratory abnormalities shall be reported to the Sponsor

according to the reporting requirements and within the time periods specified in the protocol. All AEs will be followed up until resolved or as clinically required.

Specific information about secondary malignancies such as leukaemia, MDS and aplastic anaemia or any other malignancy, will be collected up to 5 years after study medication administration or relapse of disease, including information about treatment given to the patient due to NHL. See also paragraph on Adverse Events of Special Interest in [Section 13.1.7](#).

Death is not defined as an AE but as an outcome of an AE. It is important that the event leading to the death is reported. If death is the outcome of an AE, it will be reported as such for (i) all AEs regardless of relationship to study treatment up to 12 weeks after the last administration of study treatment and (ii) AESI, and study treatment related AEs and SAEs with onset >12 weeks after the last administration of study treatment.

Progression of disease:

- **Part A:** Progression of disease will be reported as an AE until Week 12. Thereafter progression of disease will be recorded in the eCRF and still used as an efficacy endpoint. It will be the SRC who will decide if a fatal outcome of disease progression should be considered as an expected AE. This will depend on the information received and medical consideration.
- **Part B and C:** Disease progression is not reported as an AE if it is clearly consistent with the suspected progression as determined by the protocol. Hospitalisation due solely to disease progression should NOT be reported as a SAE. Any associated symptoms may be reported as adverse events if there is any uncertainty about the symptom being exclusively due to disease progression, or if it does not fit the expected pattern of progression of the disease.

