13.3 Reporting of Serious Adverse Events

13.3.1 Investigator's Responsibilities

The investigator shall report all SAEs, regardless of suspected causality, immediately (within

24 hours of the investigator becoming aware of the event) to the Sponsor or assigned designee. The immediate report shall be followed by detailed written report(s).

SAEs will be reported in the following time periods:

- SAEs will be collected from signing informed consent to ensure that any protocol-related SAEs are collected.
- Up to 12 weeks after the last administration of study treatment, whether or not considered related to IMP.
- At any time after 12 weeks after the last administration of study treatment when it comes to the investigator's attention and is judged to be related to the patient's participation in the study or related to IMP.

Any SAEs experienced after this 12 week period should only be reported to the Sponsor or assigned designee if the investigator suspects a causal relationship to the study treatment, or if it is an AESI (see [Section 13.1.7](#)). Recurrent episodes, complications or progression of the initial SAE must be reported as follow-up to the original episode within 24 hours of the investigator receiving the follow-up information. An SAE occurring at a different time interval or otherwise considered completely unrelated to a previously reported one should be reported separately as a new event.

All SAEs must be reported to Sponsor or assigned designee as follows:

1. Immediately (within 24 hours of discovery of the event) report the event by email, telephone or fax.
2. Complete the SAE report form and send within 3 working days of the discovery of the event.
3. Follow-up the SAE until resolved or as clinically required, all follow-up evaluations must be reported.
4. Record the SAE in the patient eCRFs provided.
5. Document the SAE in the hospital records.

It is important to send "as complete as possible" a report within the timelines. Incomplete information must NOT delay reporting of SAEs. Additional information must be reported once it is available; in follow-up reports using the same SAE forms, but marked as a follow-up report. In Part A, SAEs/SUSARs will be reviewed by both the SRC and the Sponsor.

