14.1.10 Analysis of Safety Data

Standard safety listings will be provided for treatment exposure, patient disposition, AEs, AEs leading to discontinuation, SAEs, laboratory safety data (serum chemistry and haematology), vital signs, 12-lead ECG, physical examination, ECOG performance status, and long-term toxicity. i.e. all safety parameters mention in [Section 13](#).

The incidence of AEs will be tabulated and reviewed for potential significance and clinical importance. The number of patients reporting AEs, and the number of AEs reported will be presented. AEs will be coded using MedDRA and graded according to CTCAE. The events will be tabulated by system organ class, preferred term, CTCAE grading, severity, and relationship to study medication. Start of AE after study medication injection and duration of AEs will also be tabulated. SAEs will also be presented in separate tabulations.

For laboratory data, the number of abnormal and clinically significant observations will be listed by patient and by time of measurement. The laboratory values will also be graded according to toxicity graded as CTCAE. All patients who receive any amount of the study

medication will be evaluated for toxicity.

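### SAP Table 6 stops the drug-related and CTCAE-grade adverse event tables at Day 92, so later related events are tabulated without relatedness or grade

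*SAP*

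**What the plan says.** SAP 3.8.1.3 sets two onset windows, Day 1 onwards and Day 1 to Day 92, and Table 6 marks which summaries are produced for each. The rows "Study drug related TEAEs (Betalutin, rituximab or lilotomab" and "Serious study drug related TEAEs (Betalutin, rituximab or lilotomab" are marked only for the window ending at Day 92, and so is the row by CTCAE grade.

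The definition behind the related rows has no end date: "A treatment related TEAE is defined as a TEAE that is possibly or probably or definitively/certainly related to the study treatment" (SAP 3.8.1.1). The same section recognises a later period: "Post Betalutin follow-up period: any AE which starts more than 92 days after the start of Betalutin".

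On collection, protocol 13.2 states: "After 12 weeks post last administration of study treatment, only new onset AESIs, and study treatment-related AEs and SAEs must be reported". Protocol 13.3.1 keeps related SAEs reportable "At any time after 12 weeks after the last administration of study treatment when it comes to the" investigator's attention. On analysis, protocol 14.1.10 states: "The events will be tabulated by system organ class, preferred term, CTCAE grading, severity, and relationship to study medication". It sets no onset limit.

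The AE listing is complete and carries "an AESI flag, the time of onset and cessation of event relative to first administration" of each drug. The AESI page itself is in SAP Table 2, for which only raw datasets are supplied. SAP 3.10 says the analyses differ considerably from the protocol because the study ended early. It neither mentions nor explains the Day 92 limit.

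**The concern.** After 12 weeks the protocol narrows AE collection to events judged related and to events of special interest. The tables by relatedness stop at about the point where related events become most of what is still recorded. The main long-term risk named in protocol 13.1.7 is secondary malignancy, which would be expected to appear late.

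A leukaemia starting after Day 92 and judged related would be counted in Serious TEAEs (Day 1 onwards) and be absent from the serious related table (Day 1 to 92). A reader comparing the two without noticing the different windows could take it to be unrelated. The grade of any late related event would have to be found in the listing.

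**Working it through.** No design figure is at issue, so the check is a reading of Table 6 against the definitions and collection rules, with a little arithmetic.

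**1. Table 6, row by row (SAP 3.8.1.3)**

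| Summary | Day 1 onwards | Day 1 to 92 | Shows relatedness or grade |
|---|---|---|---|
| All TEAEs by SOC and PT | yes | yes | no |
| Serious TEAEs | yes | yes | no |
| Drug-related TEAEs | no | yes | relatedness |
| Serious drug-related TEAEs | no | yes | relatedness |
| TEAEs by CTCAE grade | no | yes | grade |
| Most frequent TEAEs (5% or more) | no | yes | no |

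Two of six summaries are open-ended. Of the three that show relatedness or grade, none is.

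**2. What is being collected after Day 92.** All-cause collection runs to 12 weeks after dosing: 12 x 7 = 84 days. The SAP numbers the Betalutin day as Day 1, so this is Day 85. An onset on Day 93 or later therefore falls wholly in the period when only related events and AESIs are reported. It follows that Day 92 is a sensible end for the all-cause grade table, but not for the related rows, whose collection continues.

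**3. Where a late related event still appears**
- All TEAEs by SOC and PT, Day 1 onwards: always.
- Serious TEAEs, Day 1 onwards: if serious. Protocol 13.1.7 has secondary malignancies, MDS, acute leukaemia and aplastic anaemia recorded as SAEs, so these qualify whatever the causality call.
- The full AE listing, with AESI and Day 93+ flags.

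**4. What can be recovered by subtraction.** Both open-ended tables are also produced for Day 1 to 92, and both report numbers of events. By step 2:

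events (Day 1 onwards) - events (Day 1 to 92) = late related events + late unrelated AESIs, by SOC and PT.

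This gives no grade and does not separate the two terms on the right. It also fails for patients, because a participant is counted once per PT. Hypothetical case: a patient has neutropenia starting on Day 40 and again, judged related, on Day 150. Events go from 1 to 2 (difference 1). Patients go from 1 to 1 (difference 0).

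**5. Other outputs.** Haematology summaries also stop at Day 92 (SAP 3.9.1) and deaths are listed only (SAP 3.8.2), so neither fills the gap.

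**6. Scale per patient.** The safety set size is not given. As an assumption, take the 61 patients on 40/15 in the July 2022 review (SAP 1) plus about half of the 47 randomised patients in the interim analysis, say 23, on 100/20: 61 + 23 = 84. One patient then moves an overall row by 100/84 = 1.2 percentage points. At assumed sizes of 75 and 100 the figures are 1.3 and 1.0.

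**The case against.** The strongest reply is that late related toxicity is tabulated, though not under that label. Both open-ended tables include it, the named malignancies reach the serious table, and subtracting event counts roughly recovers the late related or special-interest events. This stands, and it limits the loss to grade, the related/unrelated split and the patient count.

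The second reply is that a rationale is visible. The section heading refers to the exposure period, which SAP 3.8.1.1 ends at Day 92, and the close-out analysis guarantees only about three months of follow-up for the last patient. Percentages over unequal later follow-up are harder to read. This justifies keeping the Day 92 tables. It does not explain why two rows in the same section are open-ended and the related rows are not. A footnote deals with the unequal follow-up.

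A reader might go further and infer that the related tables understate related toxicity, or that late leukaemia drops out of the tables. The documents support neither. The Day 1 to 92 tables are correct for their stated window, and a late leukaemia is in Serious TEAEs. The misreading described above also requires the reader to overlook the window and the flagged listing. Expressing the gap as a share of follow-up covered would not help either: the figure changes with the follow-up length chosen and measures no effect.

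**Conclusion.** The point holds as a cheap improvement. Three summaries by relatedness or grade stop at Day 92, while collection of related events continues and the protocol planned those tabulations without a cut. SAP 3.10 gives no specific reason.

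The loss is confined to the grade of late related events, their separation from unrelated AESIs, and an exact count of patients. How many patients are affected cannot be told from the documents and may be none. Each would move an overall row by roughly 1.0 to 1.3 percentage points at assumed safety set sizes of 100 to 75. No primary result, test or dose decision depends on it. The conclusion rests on the Table 6 marks as printed and on sites having followed the collection rules after 12 weeks.

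**What to change.** In Table 6:
- Mark the related and serious related rows for Day 1 onwards as well as Day 1 to 92.
- Add one table of related TEAEs by worst CTCAE grade, Day 1 onwards.
- Keep the all-cause grade table at Day 1 to 92.
- Footnote the open-ended tables: after 12 weeks only related events and AESIs are collected, and follow-up beyond Day 92 is unequal between patients.

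Optionally, add one row giving n (%) of Betalutin-treated patients with any AESI. PT rows cannot be summed to patients, and SOC rows give patient counts only within one SOC.

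The cost is three additional outputs and a footnote, plus the optional row. Relatedness, grade, onset day and the AESI flag are already planned. The late counts would describe what was seen; they would not estimate risk or support a comparison of regimens. If there are no late related events, the tables would say so explicitly.
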